6.4.1. As Observed Analysis

The "as observed" strategy is used in the so-called "observed cases" or "completers" analysis ubiquitous in the literature, though is not one of the recommended strategies in the ICH E9(R1). For this analysis, only data from completers at the visit are relevant. This estimand is conditional and targets the effect of treatment conditional on completion of treatment through the timepoint of interest. As the estimand is defined for a subpopulation conditional on an ICE, it is not considered causal. A summary based on observed data at each postbaseline visit will be provided. All efficacy data will be summarized using an "as observed" analysis.

6.4.2. Last Observation Carried Forward

In this missing data approach, the values after treatment discontinuation will be made missing. All missing values will be imputed using LOCF. For patients who enrolled directly into Study KGAA per Protocol KGAA Addendum 1.1, a baseline value will be used for imputation if there is no postbaseline observation. For other patients who enrolled from a parent study, the available observations during the parent study will also be used for imputation purposes.

6.4.3. Markov chain Monte Carlo-Multiple Imputation

This method of imputing missing data will be used to implement the primary estimand of the secondary objective. This method will only be implemented for the following two analysis groups:

- 1. Patients coming from parent Study KGAD (DRM06-AD06) who were lebrikizumab Q2W responders in KGAD and then were randomized in KGAA, by treatment group in KGAA.
- Patients coming from parent Studies KGAB (DRM06-AD04) and KGAC (DRM06-AD05), received lebrikizumab 250 mg Q2W during the parent study induction period and received lebrikizumab 250 mg Q2W or lebrikizumab 250 mg Q4W during the maintenance period and are not in the escape arm.

For patients who discontinue from the study treatment due to lack of efficacy, set the patient's baseline value subsequent to this time through Week 100. The MCMC-MI will be used to handle the remaining missing data. Imputation will be conducted within each treatment group and for different parent studies (including Protocol KGAA Addendum 1.1) independently so the pattern of missing observations in 1 imputation group cannot influence missing value imputation in another. For each imputation process, 25 datasets with imputations will be calculated. The initial seed values are given in Table KGAA.6.4. The SAS PROC MI with MCMC option will be used to conduct the MCMC-MI. Each complete data set will be analyzed with the specified analysis. The results from these analyses will be combined into a single inference using SAS PROC MIANALYZE.

For binary responses related to EASI and IGA, the binary response variables will be calculated based on the multiply imputed datasets that have been created. As the MCMC algorithm is based on the multivariate normal model, imputed values for IGA will not generally be one of the discrete values used in IGA scoring (0, 1, 2, 3, or 4). Therefore, to derive the binary IGA response variable, standard rounding rules will be applied to the imputed values. For example, if a patient has an IGA score imputed as 1.4 (and assuming a baseline IGA score of 3), the imputed value would be rounded down to 1, and the minimum change from a baseline of 2 would have been met. This patient would be considered a responder.

For derivation of an EASI-75 and EASI-90 response, no rounding will be performed. The imputed EASI value will be compared directly to the observed Baseline EASI value to determine whether a reduction of at least 75% or 90% was achieved.

The approach to handling missing data for Pruritus NRS, Skin Pain NRS, and Sleep-loss are the same. We use Pruritus NRS as an example. For derivation of the following Pruritus NRS responses, no rounding will be performed. The imputed Pruritus NRS value will be compared directly to the observed mean baseline Pruritus-NRS value to determine whether a response was achieved:

Percentage of patients with a Pruritus NRS of \geq 4-points at Baseline who achieve a \geq 4-point reduction from Baseline.

Imputation of continuous data will parallel that of binary variables. The imputed values will be used for the secondary endpoints such as:

- Percentage change in Pruritus NRS score from Baseline to Week 52 (for studies in which these data were collected).
- Percentage change in EASI score from Baseline at each visit.

Table KGAA.6.4. Seed Values for MCMC-Multiple Imputation

Analysis	Seed values
IGA and its related derived endpoints.	724145708
EASI and its related derived endpoints.	175356158
Pruritus NRS and its related derived endpoints.	1339532552
Sleep-lose due to pruritus and its related derived endpoints.	234325234
Skin Pain NRS and its related derived endpoints.	454236342

Abbreviations: EASI = Eczema Area and Severity Index score; IGA = Investigator's Global Assessment for AD; MCMC = Markov Chain Monte Carlo; NRS = Numeric Rating Scale.

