6.2.2. Estimands of Secondary Objectives (Efficacy)

The secondary clinical question of interest is: what is the proportion of patients who meet the clinical requirements for response AND without discontinuation due to lack of efficacy?

The primary estimand of the secondary objective is described by the following attributes:

- A. Population: modified intent-to-treat (mITT) population as defined in Section 6.1.1;
- B. Variable: apply to all secondary endpoints.
- C. How to account for intercurrent events (ICEs):
 - a. Subjects who discontinued treatment due to lack of efficacy during Study KGAA will be considered as treatment failures, that is, nonresponders, after the ICEs. Therefore, a composite strategy will be used for these types of ICEs.
 - b. For subjects who discontinued treatment due to any other reasons, the hypothetical strategy will be used to estimate what the treatment effect would have been if subjects continued with treatment. Therefore, the hypothetical strategy will be used for these ICEs
- D. Population-level summary: response proportions or means.

The **first supportive estimand of the secondary objective** is described by the following attributes:

- A. Population: mITT population as defined in Section 6.1.1;
- B. Variable: apply to all secondary endpoints.
- C. How to account for ICEs: as observed strategy will be used, that is, only data from completers at the visit are relevant.
- D. Population-level summary: response proportions or means.

The **second supportive estimand of the secondary objective** is described by the following attributes:

- A. Population: modified ITT population as defined in Section 6.1.1;
- B. Variable: apply to all secondary endpoints.
- C. How to account for ICEs: for subjects who discontinue treatment, the hypothetical strategy will be used to estimate what the treatment effect would have been if all subjects adhered to the treatment. Therefore, the hypothetical strategy is used for these types of ICEs.
- D. Population-level summary: response proportions or means.

Analytical details on how missing data, including data missing as a result of intercurrent events, will be handled can be found in Section 6.4. Endpoints will be analyzed as described in Section 6.11 and Section 6.14. No statistical test will be performed.

Table KGAA.6.2. summarizes different analyses that will be conducted on the secondary endpoints.

Table KGAA.6.2. Analysis of Secondary Endpoints

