	Treatment Discontinuation		Missing Data Imputation	
Estimand	Due to lack of efficacy	Due to any other reasons	Missing Data Imputation Method	
Primary	Composite: Set to baseline	Hypothetical: Set to missing	MCMC-MI	
Supportive	As observed	As observed	As observed analysis	
Supportive	Hypothetical: Set to missing	Hypothetical: Set to missing	LOCF	

Abbreviations: LOCF = last observation carried forward; MCMC-MI = Markov Chain Monte Carlo – Multiple imputation.

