- b MCMC-MI will be implemented for the following two analysis groups only: 1. Patients coming from parent study KGAD (DRM06-AD06) who were lebrikizumab Q2W responders in KGAD and then were randomized in KGAA, by treatment group in KGAA; 2. Patients coming from parent studies KGAB (DRM06-AD04) and KGAC (DRM06-AD05), received lebrikizumab 250 mg Q2W during parent study induction period and received lebrikizumab 250 mg Q2W or lebrikizumab 250 mg Q4W during the maintenance period and not in escape arm. For other analysis groups, As Observed will be missing data imputation method.

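### Baseline scores written in for lack-of-efficacy stops are fitted by the imputation model and lower the imputed EASI-75 and IGA 0/1 response of other dropouts; the effect is small

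*SAP*

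**What the plan says.** SAP 6.2.2 sets two targets within the primary estimand of the secondary objective. LoE stops count as failures (composite). For stops for any other reason, "the hypothetical strategy will be used to estimate what the treatment effect would have been if subjects continued with treatment". Table KGAA.6.2 carries out the LoE part as "Composite: Set to baseline", sets data after other stops to missing, and names MCMC-MI as the imputation method.

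SAP 6.4.3 fixes the order of the steps: for LoE stops, "set the patient's baseline value subsequent to this time through Week 100. The MCMC-MI will be used to handle the remaining missing data". Both groups that use MCMC-MI come from parent studies, so under 6.1.2 this is the parent-study baseline. The model is stated: "As the MCMC algorithm is based on the multivariate normal model". For EASI-75, "The imputed EASI value will be compared directly to the observed Baseline EASI value", with no rounding and no transformation named. Imputed IGA is rounded, so a value below 1.5 is a response.

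Imputation runs separately by treatment group and parent study, "so the pattern of missing observations in 1 imputation group cannot influence missing value imputation in another". On scope, footnote b to Table KGAA.6.3 says "MCMC-MI will be implemented for the following two analysis groups only": the KGAD responders randomized in KGAA, and the KGAB/KGAC patients on maintenance Q2W or Q4W outside the escape arm. Appendix 3 only describes how results are combined across the 25 datasets.

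**The concern.** A baseline score entered after an LoE stop is a way of scoring failure. It is not an outcome seen on treatment. Because it is entered before the imputation step, the normal model cannot tell it from an observed score. It raises the fitted later-visit scores and widens their spread, and both changes push the imputed scores of other-reason dropouts across the response threshold.

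Section 6.4.3 takes care that one imputation group cannot affect another, yet inside each group the two kinds of stop do affect each other. What is at stake is the EASI-75 and IGA 0/1 rates under the primary estimand in the two MCMC-MI groups. The primary safety endpoint and the As Observed and LOCF summaries are not touched.

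**Working it through.** **What the plan gives.** There is no stated figure for this effect, and no LoE rate, dropout rate, cell size, EASI distribution or list of imputation variables. The only precision figures are in the protocol addendum, section 2.13. They reproduce as p ± 1.96·√(p(1−p)/n) with n = 106: 0.83 gives 75.8% to 90.2% and 0.69 gives 60.2% to 77.8%. They do not bear on this point.

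**LoE patients themselves.** A baseline EASI means 0% change. A baseline IGA is 3 or 4 (SAP 6.8.1). Both are non-response whichever order is used, so only the other-reason dropouts can change.

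**Mechanism, in round numbers (assumed).** Take baseline EASI 29, a typical on-treatment score of 7% of baseline (0.07 × 29 = 2.03) and 5% LoE. The EASI-75 threshold is 0.25 × 29 = 7.25. Writing in the baselines raises the fitted mean by 0.05 × (29 − 2.03) = 1.35. It adds variance 0.05 × 0.95 × 26.97² = 34.6, which is an SD of 5.9, against a distance to the threshold of 7.25 − 2.03 = 5.22. This ignores the conditioning on earlier visits, so simulation is needed for the size.

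**Simulation 1.** Ten visits to Week 100, log-normal ratio to baseline EASI, about 90% EASI-75 in completers, LoE stops after loss of EASI-50 (except where the table says otherwise), random other dropout, 25 normal-model draws. The pattern is monotone, so sequential regression draws stand in for PROC MI MCMC. The two orders are the SAP order, and LoE values left out of the model with non-response assigned afterwards. Week 100 results on raw EASI:

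| Setting | LoE % | Other dropout % | Dropout EASI-75: SAP order / reordered | Shift: dropouts / group | IGA 0/1 shift: dropouts / group |
|---|---|---|---|---|---|
| n=60 | 0.0 | 24.2 | 80.3 / 80.3 | 0.0 / 0.0 | -0.1 / 0.0 |
| n=60 | 2.1 | 23.6 | 77.6 / 81.0 | -3.4 / -0.8 | -1.0 / -0.2 |
| n=60, base case | 4.7 | 23.2 | 75.5 / 82.2 | -6.7 / -1.6 | -3.0 / -0.7 |
| n=60, LoE unrelated to EASI | 4.2 | 23.7 | 68.8 / 80.2 | -11.4 / -2.7 | -4.1 / -1.0 |
| n=60, high dropout | 4.3 | 36.4 | 75.0 / 82.0 | -6.9 / -2.5 | -2.5 / -0.9 |
| n=150, stress case | 8.0 | 34.9 | 71.6 / 83.5 | -11.9 / -4.1 | -5.9 / -2.0 |

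Shifts were computed before rounding. The group shift is the dropout share times the dropout shift: 0.232 × 6.7 = 1.6 in the base case. A repeat of the base case gave -6.3 (Monte Carlo SE 0.4).

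**Simulation 2** (n=80, 17.5% other dropout, 10 imputations). At LoE 1.3 / 3.1 / 6.0%, EASI-75 shifts by -2.6 / -5.6 / -8.8 points among dropouts and -0.5 / -1.0 / -1.5 in the group. IGA 0/1 shifts by -0.7 / -1.6 / -2.4 and -0.1 / -0.3 / -0.4. An upper setting of 8.1% LoE gave EASI-75 shifts of -10.7 and -1.8. A further run gave -4.9 at 3.8% LoE and -8.1 at 7.1% (group -0.9 and -1.5).

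**MCMC check.** Data augmentation gave -8.4 (SE 1.2) at 3.2% LoE and -10.9 (SE 1.3) at 5.9% among dropouts. The direction is the same and the shifts are larger than the sequential -5.6 and -8.8, so the sequential figures may understate the effect.

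**Distance from the target, base case.** The true response of these dropouts is 88.8% if later LoE is ignored and 88.0% if it counts as failure. The SAP order gives 75.5%, which is 12.5 points below 88.0%. Reordering recovers 6.7 of these and leaves 88.0 − 82.2 = 5.8.

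**Share due to skewness.** In the repeated base case, log(EASI+1) moved the shift from -6.3 to -2.9, a reduction of 54%. Across settings a log-type scale removes roughly 40% to 70% and a square root about a fifth to a third. Percent change removes none.

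**Scale of comparison.** At n=60 and an 85% rate, the 95% half-width is 1.96·√(0.85 × 0.15/60) = 9.0 points.

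**The case against.** The clinical question in 6.2.2 is composite: "what is the proportion of patients who meet the clinical requirements for response AND without discontinuation due to lack of efficacy". A dropout who had stayed on might later have stopped for LoE, so some downward pull is legitimate. That stands, but it is small: about 0.3 to 1.6 points in most settings (0.8 in the base case) and up to about 3. It does not account for most of the shift in EASI-75.

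The same argument does succeed for continuous endpoints. At 6.0% LoE, mean percent change in EASI among dropouts was -86.0 in the SAP order and -88.0 reordered. The truth is -86.3 if later LoE counts as failure and -88.3 if it is ignored. A reader might want to reorder everything; on the composite reading these figures favour the planned order, so no claim is made there. Pruritus, sleep-loss and skin pain were not simulated.

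LoE may also be rare. The KGAD group consists of responders (5.3), the KGAB/KGAC group excludes escape-arm patients, and 5.1.2 does not say that terminations over EASI-50 are coded as LoE. A reader might infer that the reported rates are known to be too low; the documents do not show that.

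Finally, a reader might put the effect down mostly to imputing EASI on its raw scale. That goes too far. The share depends on the alternative scale, an effect remains on the log scale, and IGA 0/1 shows it with no EASI scale involved.

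**Conclusion.** The concern holds for EASI-75 and IGA 0/1 in the two MCMC-MI groups, wherever an imputation group contains LoE stops. The direction follows from the order of steps in 6.4.3 and was the same in every run with LoE present.

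The size rests wholly on assumed LoE (target rates up to about 9%, realised 1.3% to 8.1%), dropout, cell size and EASI distribution. EASI-75 shifts by roughly -3 to -12 points among other-reason dropouts and -0.5 to -3 in the group rate, about -4 in the stress case. IGA 0/1 shifts by about -1 to -6 and -0.1 to -1, about -2 in the stress case. The group shifts are smaller than the sampling error, and no tests are planned. This is a minor improvement that is cheap to make.

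**What to change.** In 6.4.3, for EASI-75 and IGA 0/1 only: set all values after any treatment discontinuation to missing, run MCMC-MI on the on-treatment data, and then assign non-response to LoE patients after their stop in each of the 25 datasets, before PROC MIANALYZE. Leave continuous endpoints as planned unless 6.2.2 is amended to say that the outcome under continued treatment ignores a later LoE failure. Report LoE and other-reason dropout counts per imputation group, so that a reader can see whether the issue arises at all.

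An optional run on a scale defined at zero, such as log(EASI+1), would show the share due to skewness; a plain log is undefined at EASI 0. Reordering alone does not remove the raw-scale shortfall.

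The cost is one extra program step or run and no new data. Table KGAA.6.4 gives one seed to EASI and everything derived from it, so EASI-75 would come from a different imputed set than the EASI change summaries, and the outputs should say so. SAP Version 3 documents analyses from a CSR approved on 22 Jan 2025. If Week 100 results are already reported, present this as a labelled sensitivity analysis beside the original.

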6.5. Multicenter Studies

This study will be conducted by multiple investigators at multiple sites internationally. The countries will be categorized into geographic regions which will be used for subgroup analyses, as described in Section 6.15.

6.6. Multiple Comparisons/Multiplicity

No statistical tests will be performed.

6.7. Patient Disposition

The following patient disposition summaries will be provided (details of the analysis populations can be found in Section 6.1.1):

- Total number and percentage of patients entering each statistical analysis population are defined in Section 6.1.1 (Analysis Population: All Entered Patients).
- The number and percentage of patients who entered the study, were assigned to treatment, and screen failed will be provided overall and by screen fail reason (Analysis population: All Entered Patients).

- The number and percentage of patients who were assigned to treatment completed treatment, the number and percentage of patients who discontinued the treatment at any time, by the assigned treatment group, and the primary reason for discontinuation of treatment (Analysis population: mITT).
 - o The primary endpoint of Study KGAA is the proportion of patients discontinued from study treatment due to AEs through the last treatment visit.
- The number and percentage of patients who were assigned to treatment completed the study (including the safety follow-up period), and the number and percentage of patients who discontinued the study at any time, by the assigned treatment group and the primary reason for discontinuation. Of the patients who discontinued the study at any time, the number and percentage of patients who completed the safety follow-up period (Analysis population: mITT).

All patients who were assigned treatment (that is, in the ITT population) and discontinued from study treatment will be listed together with the discontinuation reason, and the timing of discontinuation from the study will be reported.

Patient allocation by region, country, and center/site will be summarized with the number of patients who entered the study, number of mITT patients for each treatment group, number of patients discontinued from study treatment, and number of patients discontinued from the study. This information will be summarized overall, for adults and adolescents.

6.8. Patient Characteristics

6.8.1. Demographics and Baseline Characteristics

Patient demographic variables and baseline characteristics will be summarized by treatment group for the mITT population and the modified safety population. The continuous variables will be summarized using descriptive statistics and the categorical variables will be summarized using frequency counts and percentages.

The following demographic information will be included:

- age
- age group (adolescents [from 12 up to 18], adults 18 and over)
- age group (adolescents [from 12 up to 18], adults 18 up to 65, from 65 up to 75, 75 and over)
- sex (male, female)
- race (American Indian or Alaska Native, Asian, Black or African American, Native Hawaiian or Other Pacific Islander, White, Multiple, Other, Not Reported)
- ethnicity for the United States (US) patients (Hispanic or Latino, Not Hispanic or Latino, Not reported, Unknown)
- region (US, European Union [EU], Rest of World)
- country
- weight (kg)
- weight category (under 60 kg, from 60 up to 100 kg, at least 100 kg)
- height (cm)
- body mass index (BMI) (kg/m²)

• BMI category: underweight (less than 18.5 kg/m²), normal (from 18.5 up to 25 kg/m²), overweight (at least 25 and up to 30 kg/m²), obese (at least 30 and up to 40 kg/m²), and extreme obese (at least 40 kg/m²).

By-patient listings of basic demographic information for the ITT population will be provided.

The following baseline disease/clinical characteristics will be included:

- Age at onset (years): calculated as the difference between the date of onset of AD and the date of birth collected on the case report form (CRF).
- Duration since AD onset (years): for patients who enrolled from parent studies, it is calculated as the difference between the date of informed consent in the parent study and the date of onset of AD collected on the CRF from the parent study. For patients who enrolled directly per Protocol KGAA Addendum 1.1, it is calculated as the difference between the date of informed consent in Study KGAA and the date of onset of AD collected on the Study KGAA CRF.
- Duration since AD onset category (0 to up to 2 years, 2 to up to 5 years, 5 to up to 10 years, 10 to up to 20 years, at least 20 years)
- Anatomical area affected by AD
 - o head
 - o trunk (internal/medial axillae and groin)
 - o upper extremities (includes external axillae)
 - o lower Extremities (includes buttocks and feet), and
 - o at least 2 areas
- AD treatment used in the past (for patients with a parent study, AD history drug use was assessed at parent study screening. Plus, use of these drugs during the parent studies was recorded)
 - o none
 - o TCS
 - o TCI
 - immunosuppressive/immunomodulating drugs: systemic corticosteroids; cyclosporine; mycophenolate-mofetil; IFN-γ; janus kinase inhibitors; azathioprine; methotrexate
 - o phototherapy
 - o photochemotherapy (PUVA)
 - o other Biologics (for example, cell depleting biologics), and
 - o other non-Biologic medication/treatment
- IGA for AD score: 3 versus 4
- EASI score
- Body Surface Area (BSA)
- Pruritus NRS
- Pruritus NRS: less than 4, at least 4
- Sleep-loss due to pruritus
- Sleep-loss due to pruritus: less than 2, at least 2
- POEM
- Skin Pain NRS, and

• Skin Pain NRS: less than 4, at least 4.

The baseline definition of all demographics and baseline characteristics is summarized in Table KGAA.6.5.

Table KGAA.6.5. Patient Characteristics Baseline

	Baseline Su	ımmary
Variable	Parent Studies ^a	KGAA
Basic demograp	hic information	
Age, Age groups	X	
Sex	X	
Race	X	
Ethnicity for US patients	X	
Region	X	
Country	X	
Weight, Weight category		X
Height		X
BMI, BMI category		X
Baseline disease/clii	nical characteristics	
Age at onset (years)	X	
Duration since AD onset (years), Duration since AD onset category	X	
Anatomical area affected by AD	X	
AD treatment used in the past	X	
Immunosuppressive/immunomodulating drugs	X	
IGA for AD score	X	
EASI score	X	
BSA	X	
Pruritus NRS, Pruritus NRS category	X	
Sleep-loss due to pruritus, Sleep-loss due to pruritus	X	
category		
POEM	X	
Skin Pain NRS, Skin Pain NRS category	X	

Abbreviations: AD = atopic dermatitis; BMI = body mass index; BSA = Body Surface Area; EASI = Eczema Area and Severity Index; IGA = Investigator Global Assessment; NRS = Numeric Rating Scale; POEM = Patient Oriented Eczema Measure.

